20.4.2 Swimmers plot

Based on the FAS, four swimmers plots will be generated for the four patient subgroups above. The following will be displayed:

- Bar length: [(Date of death or date censoring of OS follow-up) – (Date of PFS event or date of PFS censoring) + 1].
- An arrow head at the end of the bar will indicate if OS follow-up is still ongoing at data cut-off, or the point in time when a patient was censored for OS follow-up. A blunt end will indicate that the patient has died.
- Symbols will be used to indicate the initiation every new treatment line after the treatment with MOR00208 + LEN.

20.5 Relationship between LEN dose intensity and efficacy

20.5.1 DoR and ORR in subgroups of varying relative cumulative LEN exposure

Patients will be categorized according to their relative cumulative LEN dose, which will be derived as follows:

Relative cumulative LEN dose intensity = (cumulative total used dose / reference cumulative dose) x 100.

- The reference cumulative dose represents the cumulative LEN dose a patient is supposed take until he/she progresses per IRC (for summaries of DoR; see below) or until he/she reaches a CR or PR (for summaries of ORR; see below):
 - Example 1 for a summary of DoR: a patient who only progresses later than Cycle 12 experiences the following reference cumulative dose: 12 months x 21 days x 25 mg LEN per day = 6300 mg LEN
 - Example 2 for a summary of DoR: a patient who progresses on Cycle 7, Day 10 experiences the following reference cumulative dose: (6 months x 21 days x 25 mg LEN per day) + (10 days x 25 mg LEN per day) = 3400 mg LEN
 - Example 3 for a summary of ORR: a patient who reaches a CR at Cycle 3 Day 25 experiences the following reference cumulative dose: 3 months x 21 days = 1575 mg LEN
- The cumulative total used dose represents the cumulative LEN dose a patient has actually ingested until he/she progresses per IRC (for summaries of DoR) or until he/she

reaches a CR or PR (for summaries of ORR). The derivation of the total used dose for LEN is described in Section 8.9.6.

Based on the relative cumulative LEN dose intensity, the following patient subgroups will be defined:

- Patients with relative cumulative LEN dose intensity of <50%
- Patients with relative cumulative LEN dose intensity of 50%-80% (inclusive)
- Patients with relative cumulative LEN dose intensity of >80%

The following will be analyzed for the subgroups defined above:

- Summary of DoR including a Kaplan-Meier plot (see Section 10.3)
- Best objective response rate and rates for best response of CR/PR/SD/PD/not evaluable assessment (see Section 9)

20.5.2 Efficacy outcome for patients with defined LEN dose reductions

The following subgroups will be defined:

- Patients with no LEN dose reduction
- Patients with one LEN dose reduction to 20 mg/day
- Patients with two or more LEN dose reductions (i.e., to a maximum reduction to 15, 10, or 5 mg LEN)
- Patients who permanently discontinued LEN (directly, or after having reduced the daily LEN dose before)

Patient subgroups 1-3 are mutually exclusive and the total number of patients in the subgroups should sum up to the total number of patients in the FAS.

Based on the FAS, the following will be summarized / analyzed for each subgroup:

- Baseline characteristics as described in Section 8.5
- Best objective response rate and rates for best response of CR/PR/SD/PD/not evaluable assessment (by IRC) as described in Section 9
- DoR (by IRC) as described in Section 10.3
- PFS (by IRC) as described in Section 10.2

-
- OS as described in Section 10.4

For the endpoints DoR, PFS, and OS, Kaplan-Meier plots will be presented.

A swimmers plot will be created for all patients with at least one LEN dose reduction at any point in time. The following will apply:

- The bar length will indicate the time on treatment with any study drug (MOR00208 only, LEN only, or both drugs at the same time)
- An arrow head at the top of the bar will indicate whether the patient is still ongoing on any study drug at data cut-off
- Using different symbols and colors/shadings for the symbols, the following will be indicated for each patient:
 - Point in time (relative from baseline) and quality of the initial response (CR or PR)
 - Point in time (relative from baseline) and quality of the best response (CR or PR)
 - Point in time (relative from baseline) of LEN discontinuation
 - Point in time (relative from baseline) of progression by IRC
 - Point in time (relative from baseline) of death
 - Point in time of LEN dose reductions /LEN discontinuations (each reduction will be symbol-/color-coded individually)

20.5.3 Other analyses related to LEN dose reduction

The following will be summarized (FAS):

- Time from baseline until first/second/third/fourth LEN dose reduction or LEN discontinuation
- Number (%) of patients who experienced at least one “deepening of response” (transition from PR to CR or SD to PR or SD to CR by IRC) after having experienced at least one dose reduction

The permanent discontinuation of LEN as per protocol will be ignored (i.e., not be considered in the analysis as dose reduction or discontinuation).

A Listing will be provided for the patients in the SAF who have discontinued both MOR00208 and LEN at the same time (i.e., sequential discontinuations will not be considered). The Listing based on the SAF will display the following:

- Point in time when the TEAE happened that led to the discontinuation of treatment
- The Preferred Term that led to the discontinuation of treatment
- Point in time (relative from baseline) when individual LEN dose reductions / LEN discontinuation happened
- The response status (CR, PR, SD, PD, not evaluable; based on IRC) at the point in time when the discontinuation happened
- The overall outcome (based on the integrated overall clinical assessment) of all central tumor response assessments

20.6 Efficacy analyses for the subgroup of patients confirmed as DLBCL by central pathology based on the FAS

Patients with a Non-Hodgkin Lymphoma category of “DLBCL” by central pathology as defined in Section 17.8 will be considered. All analyse will be based on the FAS.

20.6.1 Efficacy analyses based on all patients centrally confirmed as DLBCL

The following will be summarized / analyzed based on the IRC:

- Disease control rate (see Section 10.1)
- Time to progression including a Kaplan-Meier plot (see Section 10.5)

20.6.2 Efficacy analyses for patient subgroups within the subgroup of patients classified as DLBCL as per central pathology

IPI subgroups (low risk + low-intermediate risk vs. intermediate-high + high risk)

- ORR and rates for best response categories (CR/PR/SD/PD/not evaluable) by IRC (see Section 9)
- PFS by IRC (see Section 10.2)
- OS (see Section 10.4)

For the endpoints PFS and OS, Kaplan-Meier curves will be provided.

Prior treatment lines subgroups (1 prior treatment line vs. ≥ 2 prior treatment lines)

-
- ORR and rates for best response categories (CR/PR/SD/PD/not evaluable) by IRC (see Section 9)

Primary refractoriness subgroups (refractory vs. non-refractory)

- PFS by IRC (see Section 10.2)
- OS (see Section 10.4)

Kaplan-Meier plots will be presented.

Last line refractoriness subgroups (refractory vs. non-refractory)

- PFS by IRC (see Section 10.2)
- OS (see Section 10.4)

Kaplan-Meier plots will be presented.

Rituximab refractoriness subgroups (refractory vs. non-refractory)

- PFS by IRC (see Section 10.2)
- OS (see Section 10.4)

Kaplan-Meier plots will be presented.

Age subgroups (≤ 70 vs. > 70 years of age)

- PFS by IRC (see Section 10.2)

A Kaplan-Meier plot will be presented.

Forest plot

Forest plots for various endpoints will be generated, displaying the following biomarker and non-biomarker subgroups in one and the same illustration:

- Non-biomarker subgroups:
 - IPI subgroups dichotomized: low and low-intermediate vs. high-intermediate and high
 - Gender: female vs. male
 - Rituximab refractoriness: yes vs. no

-
- Refractoriness to last prior treatment line: yes vs. no
 - Primary refractoriness: yes vs. no
 - Prior autologous stem cell transplantation: yes vs. no
 - Number of prior treatment lines dichotomized: 1 vs. ≥ 2
 - Age dichotomized: ≤ 70 years vs. > 70 years of age
 - Biomarker subgroups:
 - NK cell numbers at baseline: < 100 vs. ≥ 100 cells/ μ l
 - Cell of origin by IHC: GCB vs. non-GCB vs. unknown

The following Forest plots displaying an estimate for the expectation together with 95% confidence intervals will be generated:

- Forest plot for ORR (by IRC)
- Forest plot for CR rate (by IRC)
- 24-month PFS rate (by IRC)
- 24-month DoR rate (by IRC)
- 24-month OS rate
- 30-month PFS rate (by IRC)
- 30-month DoR rate (by IRC)
- 30-month OS rate (by IRC)

20.7 Additional subgroup analyses

20.7.1 Efficacy analyses in subgroups of patients enrolled at sites that enrolled ≤ 3 vs. > 3 patients

The following subgroups will be defined:

- Sites recruiting ≤ 3 patients
- Sites recruiting > 3 patients

The following will be summarized / analyzed by subgroup based on the FAS:

- ORR and rates for best response categories (CR/PR/SD/PD/not evaluable) by IRC (see Section 9)

-
- OS (see Section 10.4)
 - Duration of CR (by IRC; Section 10.3.5)

For the endpoints OS and Duration of CR, a Kaplan-Meier plots will be presented.

ORR by site

An analysis on ORR as specified in Section 9 will be also conducted for individual sites that had recruited at least one patient.

20.7.2 Efficacy analyses in subgroups of patients recruited at US sites vs. European sites

The following subgroups will be defined:

- Patients recruited at sites in the USA (US sites)
- Patients recruited at European sites

The following will be analyzed / summarized based on the FAS:

- ORR and rates for best response categories (CR/PR/SD/PD/not evaluable) by IRC (see Section 10.1)
- OS (Section 10.4)
- Duration of CR (by IRC; Section 10.3.5)

For the endpoints OS and duration of CR, Kaplan-Meier plots will be produced.

20.7.3 Efficacy analyses for histological subgroups of NHL

Section 17.3 specifies the analyses of ORR, DoR, OS, and PFS for the NHL subtypes DLBCL- NOS (=DLBCL, not further specified) and Composite Lymphoma as determined by central pathology. The following will be added:

- All analyses will be additionally be produced based on the SAF
- Kaplan-Meier plots will be produced for endpoints DoR, OS, PFS for both FAS and SAF

20.7.4 Listings displaying best response and DoR by NHL subtype

Based on the SAF, a Listing will be produced displaying the following:

-
- Best response by IRC
 - DoR per IRC including the following:
 - Information whether the DoR follow-up has discontinued due to PD
 - Information whether the patient has been censored including the reason for censoring
 - Best response by INV
 - DoR per INV including the following:
 - Information whether the DoR follow-up has discontinued due to PD
 - Information whether the patient has been censored including the reason for censoring

Based on the SAF, another Listing will be produced displaying the following:

- PFS time and the information if the patient was censored or had a PFS event by IRC
- PFS time and the information if the patient was censored or had a PFS event by INV
- OS time and the information if the patient was censored or had an OS event

20.7.5 Baseline characteristics of various patients subgroups

The baseline characteristics as outlined in Section 8.5 will be summarized for the following subgroups:

- Patients ≤ 70 years of age: based on the FAS
- Patients > 70 years of age: based on the FAS
- Patients confirmed as DLBCL as per central pathology (i.e., patients with a Non-Hodgkin Lymphoma category of "DLBCL" by central pathology as defined in Section 17.8 will be considered): based on the FAS
- Patients confirmed as DLBCL as per central pathology (i.e., patients with a Non-Hodgkin Lymphoma category of "DLBCL" by central pathology as defined in Section 17.8 will be considered): based on the SAF

20.8 Efficacy analyses based on the SAF

20.8.1 Summaries

The following endpoints will be analysed / summarized:

-
- ORR and rates for best response categories (CR/PR/SD/PD/not evaluable) by IRC (see Section 10.1)
 - DoR (by IRC; see Section 10.3)
 - DoR (by IRC) by best response (by IRC)
 - PFS (by IRC; Section 10.2)
 - OS (Section 10.4)

For the endpoints DoR, DoR by best response, PFS, and OS, Kaplan-Meier plots will be generated.

20.8.2 Forest plots

Forest plots for various endpoints will be generated, displaying the following biomarker and non-biomarker subgroups in one and the same illustration:

- Non-biomarker subgroups:
 - IPI subgroups dichotomized: low and low-intermediate vs. high-intermediate and high
 - Gender: female vs. male
 - Rituximab refractoriness: yes vs. no
 - Refractoriness to last prior treatment line: yes vs. no
 - Primary refractoriness: yes vs. no
 - Prior autologous stem cell transplantation: yes vs. no
 - Number of prior treatment lines dichotomized: 1 vs. ≥ 2
 - Age dichotomized: ≤ 70 years vs. > 70 years of age
- Biomarker subgroups:
 - NK cell numbers at baseline: < 100 vs. ≥ 100 cells/ μ l
 - Cell of origin by IHC: GCB vs. non-GCB vs. unknown

The following Forest plots displaying an estimate for the expectation together with 95% confidence intervals will be generated:

- Forest plot for ORR (by IRC)
- Forest plot for CR rate (by IRC)
- 24-month PFS rate (by IRC)

-
- 24-month DoR rate (by IRC)
 - 24-month OS rate
 - 30-month PFS rate (by IRC)
 - 30-month DoR rate (by IRC)
 - 30-month OS rate (by IRC)

20.8.3 Analyses for the subgroup of patients confirmed as DLBCL by central pathology based on the SAF

Patients with a Non-Hodgkin Lymphoma category of “DLBCL” by central pathology as defined in Section 17.8 will be considered.

Summaries

The following endpoints will be analysed / summarized:

- ORR and rates for best response categories (CR/PR/SD/PD/not evaluable) by IRC (see Section 9.1)
- DoR (by IRC; Section 10.3)
- DoR (by IRC) by best response (by IRC)
- PFS (by IRC; Section 10.2)
- OS (Section 10.4)

For the endpoints DoR, DoR by best response, PFS, and OS, Kaplan-Meier plots will be generated.

Summaries for the subgroup of primary refractory patients within the subpopulation of DLBCL

- ORR and rates for best response categories (CR/PR/SD/PD/not evaluable) by IRC (see Section 9.1)
- DoR (by IRC; Section 10.3)

For DoR, a Kaplan-Meier graph will be produced.

Forest plots

Forest plots for various endpoints will be generated, displaying the following biomarker and non-biomarker subgroups in one and the same illustration:

- Non-biomarker subgroups:
 - IPI subgroups dichotomized: low and low-intermediate vs. high-intermediate and high
 - Gender: female vs. male
 - Rituximab refractoriness: yes vs. no
 - Refractoriness to last prior treatment line: yes vs. no
 - Primary refractoriness: yes vs. no
 - Prior autologous stem cell transplantation: yes vs. no
 - Number of prior treatment lines dichotomized: 1 vs. ≥ 2
 - Age dichotomized: ≤ 70 years vs. > 70 years of age
- Biomarker subgroups:
 - NK cell numbers at baseline: < 100 vs. ≥ 100 cells/ μ l
 - Cell of origin by IHC: GCB vs. non-GCB vs. unknown

The following Forest plots displaying an estimate for the expectation together with 95% confidence intervals will be generated:

- Forest plot for ORR (by IRC)
- Forest plot for CR rate (by IRC)
- 24-month PFS rate (by IRC)
- 24-month DoR rate (by IRC)
- 24-month OS rate

20.9 PFS and DoR analyses applying alternative censoring rules

Analyses for the endpoints PFS and DoR will be performed using alternative censoring rules, i.e., three scenarios that led to censoring as per Table 13 will be considered as a PFS event.

Situation	Outcome as per main analysis (see Table 13)	Censoring date as per main analysis (see Table 13)	Outcome as per alternative censoring rules	Date of progression as per alternative censoring rules
Discontinued the	Censored	Date of last	Event	Date of

STATISTICAL ANALYSIS PLAN

 MorphoSys AG
 MOR208C203

Situation	Outcome as per main analysis (see Table 13)	Censoring date as per main analysis (see Table 13)	Outcome as per alternative censoring rules	Date of progression as per alternative censoring rules
study with no event		adequate tumour assessment		discontinuation of the study drug that was discontinued latest*
Patient received non-study anti-DLBCL treatment before disease progression	Censored	Date of last adequate tumour assessment before start of non-study cancer treatment	Event	Date of initiation of non-study anti-DLBCL treatment
Death or progression after two or more missed visits	Censored	Date of last adequate tumour assessment	Event	Date of the first missed tumour assessment (i.e., the planned date of the assessment that was missed)

*Note: in L-MIND, PFS follow-up stops with treatment discontinuation (a post-treatment PFS follow-up is not conducted in L-MIND).

The censoring strategy for the remaining scenarios described in Table 13 will still apply.

The following analyses applying the alternative censoring rules will be conducted:

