5.3.2 End of Study

The end of the study is defined as the date of the last visit of the last patient completing 5 years study duration. If any patient is on treatment at the end of the study and MOR00208 is not yet commercially available, patients will be switched to alternative methods of supply with MOR00208, upon assessment of a clinical benefit of continued treatment by the investigator, and in accordance with the local regulatory guidance. Upon study closure, MorphoSys will notify the applicable regulatory agencies in accordance with local requirements.

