5.4.3 Final analysis

The final analysis will be performed when all patients have performed their End of Treatment visit. The analyses will be conducted after database lock. All study results will be made available to MorphoSys AG prior to completion of the final CSR.

MorphoSys may perform further exploratory analyses to investigate correlations between different biomarker and response variables. Any post-hoc, exploratory analyses completed to support planned study analyses, which were not identified in this SAP, will be documented and reported in appendices to the CSR, but will not necessitate an update of the final SAP. Any results from these unplanned analyses (post-hoc) will also be clearly identified in the text of the CSR.

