**Table 13: Censoring Rules**

Situation	Date of Progression or Censoring	Outcome	Censoring reason
Ongoing and No event until data cut-off	Date of last adequate tumour assessment	Censored	Ongoing
Discontinued the study with no event	Date of last adequate tumour assessment	Censored	Discontinued without event
No baseline tumour assessment	Date of C1D1	Censored	No baseline tumour assessment
Lost to follow-up	Date of last IRC tumour assessment (or C1D1 in case of study discontinuation w/o progression before any post-baseline assessment)	Censored	Lost to follow-up
Patient received non-study anti-DLBCL treatment before disease progression	Date of last adequate tumour assessment before start of non-study cancer treatment	Censored	New anti-cancer therapy started
Clinical Progression*	Date of last adequate tumour assessment	Censored for Analysis based on Investigator assessment only	Clinical Progression not validated by Cheson Criteria
PD by modality not including PET Scan is not confirmed by modality including PET Scan**.	Date of last adequate tumour assessment	Censored for Analysis based on Investigator assessment only	Non-PET PD not confirmed by PET.
Death before any date of PD assessment	Date of death	Progressed	
Death between adequate assessments	Date of death	Progressed	
Death or progression after two or more	Date of last adequate	Censored	Event documented

STATISTICAL ANALYSIS PLAN

 MorphoSys AG
 MOR208C203

Situation	Date of Progression or Censoring	Outcome	Censoring reason
missed visits	tumour assessment		after two or more missing tumor assessments
EOT after two or more missed assessments without disease progression	Date of Last adequate Tumour Assessment	Censored	Adequate assessment no longer available

Abbreviations: EOT = End of Treatment; IRC = Independent Review Committee; PD = progressive disease; CT = Computed tomography; PET = Positron emission tomography. *Progression as per Investigator's assessment and without meeting PD criteria according to Response Criteria for Malignant Lymphoma (Cheson et al., 2007). **The rule only applies in case a PET-including modality is performed after a non-PET including modality.

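### The alternative PFS/DoR rule in SAP 20.9 does not exempt administrative end of study, so patients still progression-free at closure can be counted as progressed in the final analysis

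*SAP*

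**What the plan says.** Table 13 of the SAP sets the main censoring rules for PFS, and SAP 10.3.3 applies them to DoR. A patient in the row "Discontinued the study with no event" is censored at the last adequate tumour assessment. A separate row, "Ongoing and No event until data cut-off", is also censored.

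SAP 20.9 (Addendum 5.0) defines alternative analyses in which "three scenarios that led to censoring as per Table 13 will be considered as a PFS event". The three are discontinuation of the study without an event, non-study anti-DLBCL treatment before progression, and death or progression after two or more missed visits. For the first, the event date is the "discontinuation of the study drug that was discontinued latest". The section adds that "The censoring strategy for the remaining scenarios described in Table 13 will still apply". The rule feeds four PFS and four DoR analyses (SAP 20.9.1 and 20.9.2), each with Kaplan-Meier graphs.

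On timing, SAP 5.4.3 states: "The final analysis will be performed when all patients have performed their End of Treatment visit". SAP 7.4 sets the final cut-off at the latest termination visit among the patients, and SAP 7.5 places the final lock after all patients have discontinued the study. Protocol 5.3.2 ends the study at the last visit of the last patient to complete 5 years. If a patient is then still on treatment, MOR00208 is not commercially available and the investigator sees clinical benefit, "patients will be switched to alternative methods of supply with MOR00208".

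**The concern.** SAP 20.9 appears meant to ask whether stopping or switching treatment hides progression. SAP 20.9 itself notes that there is no PFS follow-up after treatment, so counting drop-out as failure is a reasonable stress test. Leaving because the sponsor closes the study says nothing about the patient's lymphoma, yet the rule draws no distinction.

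The patients affected would be those with the longest disease control. If they are coded as events, the far end of the alternative PFS and DoR curves records when the study closed, and a median that lymphoma had not produced could be produced by the closure date.

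**Working it through.** The plan gives no figure for this, so there is none to reproduce. The check has two parts.

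**1. Where does a patient who is progression-free on drug at closure fall in Table 13?**

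- The ongoing row: SAP 5.4.3, 7.4 and 7.5 together mean every patient has terminated by the final cut-off, so this row is essentially empty.
- A completer row: none exists.
- Lost to follow-up: does not describe a patient who attends to the end.
- "EOT after two or more missed assessments without disease progression": applies only if two or more assessments were missed. It stays censored under 20.9. No precedence is given if a patient fits both this row and the discontinued row.
- "Discontinued the study with no event": fits literally, given that SAP 7.5 describes all patients as having discontinued. Under 20.9 this is an event.

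For a patient transferred to other supply, MOR00208 is not actually stopped, so the 20.9 event date is also unclear.

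**2. How large could the effect be?**

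Inputs from the documents: about 80 patients (SAP 5.3); a month of 30.4375 days (SAP 6.6); yearly scans from Cycle 25 Day 1, i.e. 24 × 28 / 30.4375 = 22.1 months, then 34.1, 46.1, 58.1 and 70.1; study end tied to 5 years, i.e. 5 × 12 = 60 months.

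Assumptions: *k* patients are progression-free on drug at closure, leaving evenly over 60–84 months; the other 80 − *k* have genuine events spread evenly over 1.5–40 months; no other drop-out.

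With no earlier censoring, Kaplan-Meier after the genuine events is *k*/80. If closure patients are censored, it stays there. If they are events, the last patient at risk contributes a factor 1 − 1/1 = 0 and the curve ends at zero.

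| *k* | Events: exempted / literal 20.9 | 48-month PFS (both) | Final PFS: exempted / literal | Median, months: exempted / literal |
|---|---|---|---|---|
| 16 | 64 / 80 | 0.20 | 0.20 / 0.00 | 25.3 / 25.3 |
| 24 | 56 / 80 | 0.30 | 0.30 / 0.00 | 28.8 / 28.8 |
| 32 | 48 / 80 | 0.40 | 0.40 / 0.00 | 33.4 / 33.4 |
| 44 | 36 / 80 | 0.55 | 0.55 / 0.00 | not reached / 61.7 |

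In the last row the literal median needs four closure events to bring 44/80 down to 40/80. The fourth falls at 60 + 3 × 24/43 = 61.7 months.

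Earlier drop-out acts separately. With *k* = 24 and 10 drop-outs before closure, the 48-month rate is 0.361 under Table 13 and 0.300 under 20.9, with or without the exemption; the medians are 32.3 and 27.2. That shift is what 20.9 is designed to show, and the exemption keeps it.

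For DoR, assume 40 responders, genuine events over 2–36 months and closure at 58–82 months from response. With 16 or 20 still responding, the median is unchanged (30.1 and 36.0). With 24 or 28, not reached becomes 58 + 3 × 24/23 = 61.1 and 58 + 7 × 24/27 = 64.2 months.

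**The case against.** A reader might infer that every patient progression-free at closure is counted as progressed. The documents do not go that far. SAP 6.10 names study completion and study discontinuation separately, and nothing says that a completer belongs in the discontinued row. Patients who fit the lost-to-follow-up row, or the row for End of Treatment after missed assessments, stay censored. The transfer in Protocol 5.3.2 is conditional. The SAP is written against protocol Amendment 3.0, whereas the protocol in hand is Amendment 5. All of this stands, and it is why the point says that patients can be counted.

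SAP 20.9 also states no cut-off. Its addendum works with 24- and 30-month landmarks, and Addendum 8.0, which adds 48-month outputs, does not ask for 20.9 to be repeated. At any earlier cut-off, treated patients are ongoing and remain censored. This stands too: the problem arises only if 20.9 is run at the final analysis. Nothing limits it to an earlier one.

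A second tempting inference is that the analysis stops testing informative censoring. It does not. Up to about 60 months the rule does its intended work, and main PFS and DoR still censor these patients.

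These arguments limit the effect but do not answer the text. Neither completion nor discontinuation is defined for Table 13, and SAP 7.5 describes all patients as having discontinued, so a programmer following the SAP has good reason to code closure patients as events.

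**Conclusion.** The point holds as a gap in a stated rule that can give a wrong result, and it should be fixed. If 20.9 is run at the final analysis, patients who are progression-free at completion, closure or transfer can be counted as progressed. The effect is confined to supplementary analyses. From about 60 months the curve's tail and event count would reflect the closure date, the curve could fall to zero, and a median not reached by then could become reached. The planned 24-, 30- and 48-month rates and the main analyses are unaffected.

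The 60-month bound assumes the study runs to its planned end; a site or study terminated early under Protocol 6.9.2 would bring the dates forward. For DoR the clock starts at response, so the bound is 60 months minus time to response, and the 48-month rate is safe when response came within 60 − 48 = 12 months. The numbers of patients on drug at closure and of responders (40, against 0.35 × 80 = 28 under the design assumption) are illustrative and not taken from the plan.

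**What to change.** In SAP 20.9 and Table 13, state that patients without progression are censored at the last adequate tumour assessment when their participation or study-supplied treatment ends because of study completion, sponsor or site closure, or transfer to alternative or commercial MOR00208 supply. Leave the three converted scenarios otherwise as they are. Leave the clinical-progression row as in Table 13; it is a separate row that 20.9 does not convert. Add an order of precedence for patients who fit more than one row.

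The cost is a short SAP amendment and some mapping of end-of-treatment reasons. SAP 8.2 shows that some of these are free text, so a few cases will need individual review before lock.
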